Application of Ideal Binary Masking to Disordered Speech

NCT05244603

12/3/2019

Study Protocol

Dysarthria and hearing loss are communication disorders that can substantially reduce intelligibility of speech and the addition of background noise adds a further challenge. This proposal utilizes an established signal processing technique, currently exploited for improved understanding of speech in noise for listeners with hearing loss, to investigate its potential application to overcome speech-in-noise difficulties for listeners understanding dysarthric speech. Successful completion of this project will demonstrate proof-of-concept for the application of this signal processing technique to dysarthric speech in noise, and inform the development of an R01 proposal to perform a large-scale evaluation of the technology, and clinically meaningful implications, in a broad range of disordered speech types and severities.

Dysarthric and healthy control phrases will be processed in six different experimental conditions. Conditions 1 and 2 will consist of the unprocessed phrases representing dysarthric (condition 1) and control speech (condition 2) in quiet. Conditions 3 and 4 will consist of the phrases representing dysarthric (condition 3) and control speech (condition 4) mixed with noise at a given signal-to-noise ratio (SNR). For a masker, a cafeteria noise (Auditec of St. Louis) will be used to represent a relatively natural listening background. Conditions 5 and 6 will consist of the same phrases representing dysarthric (condition 5) and control speech (condition 6) mixed with cafeteria noise as in conditions 3 and 4, but processed by the IBM. Speech stimuli will be processed by custom MATLAB scripts and will be generated using high-quality D/A converters and a PC.

All participants will be seated in a sound treated booth and fitted with *Sennheiser HD280 Pro* circumaural headphones. Hearing-impaired participants will not wear their hearing aids during testing, but audibility will be ensured through the spectral shaping via a digital equalizer. Participants will be told that they will be presented with phrases that will be difficult to understand, either because the phrases will be produced by a person with a speech disorder and/or background noise, and that their job is to listen carefully and try to understand what is being said. The experimenter will present the phrases, one at a time, and following each phrase, the participants will be asked to repeat back what they think they heard. The experimenter will type out the participant's verbal responses. This method was selected over more traditional "hear and type" methods to mitigate possible issues with mobility and typing competencies, particularly applicable to the older listeners. Responses will be scored for words correct, using previously established scoring criteria for the semantically anomalous phrases and a validated in-house computer program.

Multiple regression analysis will be used to test for differences in PWC scores across the conditions. Each model will control for individual age, gender, and PWC scores in quiet—thereby controlling for baseline perception capabilities.

Statistical Design and Power

The outcome measure for the current study is percent words correct (PWC). To test whether there is a difference in PWC between the experimental conditions, linear mixed effects regression analysis will be used. Each mixed effects model will control for covariates including individual age, gender, MOCA score, audiometric thresholds, frequency-specific audibility of stimuli, and QuickSIN scores. We will also assess PWC scores in quiet as both a covariate and as a potential moderator—thereby controlling for baseline perception capabilities—and intra-individual variability. Of particular interest is whether the IBM-processed speech is significantly more intelligible than unprocessed speech in noise (which would indicate that IBM processing provides benefit). These models will also test whether IBM-processed speech is not significantly different from unprocessed speech in quiet (which would provide evidence that IBM processing restores intelligibility of speech in noise to that of speech in quiet). These tests will be done systematically. The first aim includes the unadjusted (bivariate) model as well as the adjusted model discussed in the Research Strategy. Aim 2 builds on this by including important moderators.

For power, we used the *simr* R package to simulate power given the sample size and expected effect sizes. This analysis relied on Monte Carlo simulations from a known population model. All code used is provided below. For Aim 1, a minimum of 30 participants will be tested per sub-experiment, as this results in sufficient power for the planned comparisons (for alpha of .05, with 6 covariates, effect size of .5, power = .93).

For Aim 2, at least 30 participants will be tested, as the power analyses with a moderate interactive effect indicate this sample size will result in sufficient power for the planned interactions (for alpha of .05, with 6 covariates, power = .91).

The R code to run the analyses are provided below.

```
library(tidyverse)
set.seed(843)

library(simr)

data_production <- function(npart = 30,          ## number of subjects
                           nplot = 6,          ## number of repeated measures
                           effect_x = .5,      ## effect of variable x
                           sigma_s = 2,         ## variance within participant
                           sigma = 1) {         ## residual variance

  x = rep(1:nplot, times = nplot)
  z = rnorm(npart*nplot)
  a = rnorm(npart*nplot)
  b = rnorm(npart*nplot)
  c = rnorm(npart*nplot)
  d = rnorm(npart*nplot)
  e = rnorm(npart*nplot)
  f = rnorm(npart*nplot)
  standeff = rep( rnorm(npart, 0, sigma_s), each = nplot)
  stand = as.character(rep(1:npart, each = nplot))
  ploteff = rnorm(npart*nplot, 0, sigma)
  resp = 1 + effect_x*x + standeff + ploteff
  dat = data.frame(x = as.character(x), z = scale(z), stand, resp = scale(resp), a, b, c, d, e, f)
  dat
}

data_production_int <- function(npart = 30,          ## number of subjects
                                 nplot = 6,          ## number of repeated measures
                                 effect_x = .5,      ## effect of variable x
                                 sigma_s = 2,         ## variance within participant
                                 sigma = 1) {         ## residual variance

  x = rep(1:nplot, times = nplot)
  z = rnorm(npart*nplot)
  a = rnorm(npart*nplot)
  b = rnorm(npart*nplot)
  c = rnorm(npart*nplot)
  d = rnorm(npart*nplot)
  e = rnorm(npart*nplot)
  f = rnorm(npart*nplot)
  standeff = rep( rnorm(npart, 0, sigma_s), each = nplot)
  stand = as.character(rep(1:npart, each = nplot))
  ploteff = rnorm(npart*nplot, 0, sigma)
  resp = 1 + effect_x*x + effect_x*x*z + effect_x*x*x*z + standeff + ploteff
  dat = data.frame(x = as.character(x), z = scale(z), stand, resp = scale(resp), a, b, c, d, e, f)
```

```

dat
}

d <- data_production()
fit <- lmer(resp ~ x + a + b + c + d + e + f + (1|stand), data = d)
fit2 <- extend(fit, along="stand", n=30)
fixef(fit2)[2:3] <- 0.15
fixef(fit2)[4:5] <- 0.30
fixef(fit2)[6] <- 0.45

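### Does using the same phrases in the noise and IBM conditions, with no stated phrase assignment or order, undermine the IBM-versus-noise contrast?

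*Combined protocol and SAP*

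**What the plan says.** The Study Protocol opens its account of the stimuli with "Dysarthric and healthy control phrases will be processed in six different experimental conditions". Two conditions are in quiet, two are mixed with cafeteria noise, and two are mixed with noise and then processed. Of the last pair it says "Conditions 5 and 6 will consist of the same phrases representing dysarthric (condition 5) and control speech (condition 6) mixed with cafeteria noise", as in the noise conditions.

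The only text on presentation is "The experimenter will present the phrases, one at a time, and following each phrase, the participants will be asked to repeat back" what they heard. Order, randomisation, counterbalancing and phrase lists are not mentioned.

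Statistical Design and Power sets the main comparison: "Of particular interest is whether the IBM-processed speech is significantly more intelligible than unprocessed speech in noise". It also asks whether IBM-processed speech differs from speech in quiet. The R code gives each participant six values, commented as "number of repeated measures".

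Two sets of adjustment variables appear. The Study Protocol regression states "Each model will control for individual age, gender, and PWC scores in quiet". The mixed model states "Each mixed effects model will control for covariates including individual age, gender, MOCA score, audiometric thresholds, frequency-specific audibility of stimuli, and QuickSIN scores". The Aim 1 power model is "fit <- lmer(resp ~ x + a + b + c + d + e + f + (1|stand), data = d", whose only random term is a listener intercept. The adjusted model is also said to be discussed in a Research Strategy, which is not part of this document.

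**The concern.** Six repeated measures and a quiet score used as a covariate suggest that each listener is tested in several conditions, probably all six. If the noise and IBM conditions also share phrases, a listener might hear a phrase in noise and later hear it after processing. Some of the later score could then be memory or practice.

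The direction depends on order. Noise before IBM flatters the processing; IBM before noise hides a real benefit. If every listener had the same order, order would coincide with condition and no covariate could separate them. Even without repeated phrases, a fixed order would mix practice, fatigue and adaptation to the talker with condition. The IBM-versus-quiet comparison is exposed in the same way. The study is a proof of concept meant to inform a larger proposal, so an artefact in the main contrast would carry forward.

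**Working it through.** **The plan's own figure.** Aim 1 power is stated as .93 for 30 participants, alpha .05 and six covariates. Re-running the Aim 1 code at its own seed, with lme4 in place of simr and 1,000 simulations, gives 0.946 with the 5-df F test and 0.953 with the likelihood-ratio test (0.957 in a second run using nlme). The figure is reproduced closely, and it does not depend on phrase assignment or order.

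**Inputs.** From the R code: slope 0.5 over conditions 1 to 6, listener SD 2, residual SD 1, 30 listeners, response scaled to unit SD. Assumed, because the plan gives no value: a second-hearing gain *g* in scaled SD units, and no true IBM effect.

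**Standard error of one IBM-versus-noise contrast.**
- Variance of the integers 1 to 6 is 2.917, so total variance = 0.5² × 2.917 + 2² + 1² = 5.729.
- Scaled residual SD = 1/√5.729 = 0.418.
- Contrast SE = 0.418 × √(2/30) = 0.108, on (30 − 1)(6 − 1) = 145 df.

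**Bias.** If *p* is the share of phrase pairs heard in noise before IBM, bias = *g*(2*p* − 1). The two-sided 5% rejection rate comes from the noncentral t with noncentrality bias/0.108.

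| Gain *g* (SD) | Noise always first (*p* = 1) | *p* = 0.75 | *p* = 0.5 |
|---|---|---|---|
| 0.05 | 7.5% | – | 5% |
| 0.10 | 15% | – | 5% |
| 0.15 | 28.2% | 10.6% | 5% |
| 0.30 | 78.9% | 28.2% | 5% |

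For example, *g* = 0.15 with noise always first has noncentrality 0.15/0.108 = 1.39 and rejection 28.2%.

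**Order randomised separately for each listener.** Simulation with 20,000 runs of 30 listeners by 6 conditions gives about 5.5% at *g* = 0.15 and 7.5% at *g* = 0.30 when the residual is pooled over all conditions. The small excess arises because the pooled residual understates the variance of this contrast. A paired test on the same data returns about 5%.

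**Asymmetric carry-over with balanced order.** If IBM-first adds 0.30 SD to noise but noise-first adds 0.15 SD to IBM, bias = 0.5 × 0.15 − 0.5 × 0.30 = −0.075 SD. Power for an assumed true benefit of 0.30 SD falls from 78.9% to 54.5%, since the expected contrast falls to 0.30 − 0.075 = 0.225. All three inputs are assumptions.

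**What the text supports.** The large entries need a listener to hear the same phrase in both conditions, together with a fixed or strongly unbalanced order. Neither is stated. The shared-phrase sentence describes how recordings are processed. Read that way, it keeps the speech material constant between noise and IBM, so that the contrast is not confounded with phrase difficulty.

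**The case for a change.** The strongest case for acting is that the silence is complete. Nothing on assignment or order appears in the procedure, the covariate lists or the code. A fixed order cannot be repaired after testing. A gain of 0.15 SD is no larger than the smallest non-zero condition effect in the sponsor's own code, yet it could lift the error rate to 28%. Stating rotated lists and a counterbalanced order would take little text and no extra listeners.

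The omission stands, and so does the arithmetic. The following limits what can be drawn from them:

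- The plan never says that order is fixed. If order varies and is recorded, a position term can be added; the covariate list is open-ended, and the coded model is a power simulation with placeholder covariates rather than a final specification.
- The plan recruits 30 participants per sub-experiment without defining that term. Six repeated measures support a fully within-listener reading but do not settle which conditions each listener meets.
- The phrases are semantically anomalous, which limits guessing from context, though it does not rule out a gain from hearing the same phrase again.
- Splitting the bank has a price. Six lists raise the phrase-sampling part of each score's standard error by √6 = 2.4 compared with using the whole bank in every condition. If dysarthric and control phrases differ in wording, three lists per speaker type would do, and the factor is √3 = 1.7. Neither bank size nor shared wording is stated, so no particular split can be shown to be better.
- A random phrase effect would need phrase-level data, whereas the code uses one score per listener per condition.

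**Conclusion.** The concern does not call for a change. The plan leaves phrase assignment and condition order unwritten, but no stated rule produces a wrong result. Bias in the IBM-versus-noise contrast requires within-listener repetition of phrases plus an unbalanced order or asymmetric carry-over (or, without repetition, a fixed order with practice effects). The document asserts none of these.

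If the worst case did hold, with noise always first, one contrast would have a false-positive rate of 7.5% to 79% for assumed gains of 0.05 to 0.30 SD. Under per-listener randomisation, the rate is about 5% to 7.5% for gains of 0.15 to 0.30 SD, and about 5% with a paired test. These figures rest on the variances in the power code and on gains that the plan does not supply. Asymmetric carry-over could still cost power under a balanced order, but only under further assumptions.

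This is a gap that investigators would ordinarily fill sensibly, or may already have filled in the Research Strategy that the plan cites.

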# summary(fit2)

broom:::augment(fit2) %>%
  ggplot(aes(factor(x), .fitted, fill = factor(x), color = factor(x))) +
  geom_boxplot(alpha = .7) +
  theme_classic() +
  scale_fill_viridis_d() +
  scale_color_viridis_d() +
  theme(legend.position = "none")

sim1 <- powerSim(fit2)
sim1

d2 <- data_production_int()
fit <- lmer(resp ~ x*z + a + b + c + d + e + f + (1|stand), data = d2)
fit2 <- extend(fit, along="stand", n=30)
fixef(fit2)[14] <- 0.2
fixef(fit2)[15] <- 0.2
fixef(fit2)[16] <- 0.3
fixef(fit2)[17] <- 0.3
fixef(fit2)[18] <- 0.4

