# summary(fit2)

broom:::augment(fit2) %>%
  ggplot(aes(z, .fitted, fill = factor(x), color = factor(x))) +
  geom_point(alpha = .7) +
  geom_smooth(method = "lm") +
  theme_classic() +
  scale_fill_viridis_d() +
  scale_color_viridis_d()

sim2 <- powerSim(fit2, test = fcompare(~ x + z))
sim2

```

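### If quiet PWC is taken from conditions 1 and/or 2, using it as a moderator biases the IBM-versus-quiet interaction downwards

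*Combined protocol and SAP*

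**What the plan says.** The Study Protocol section lists six conditions and says of the first two: "Conditions 1 and 2 will consist of the unprocessed phrases representing dysarthric (condition 1) and control speech (condition 2) in quiet". The analysis paragraph that closes that section states: "Each model will control for individual age, gender, and PWC scores in quiet".

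Under Statistical Design and Power, PWC is the outcome, and the quiet scores get a second role: "We will also assess PWC scores in quiet as both a covariate and as a potential moderator". The same paragraph says: "These models will also test whether IBM-processed speech is not significantly different from unprocessed speech in quiet". The quiet scores are therefore outcome rows in these models. On the second aim it says: "Aim 2 builds on this by including important moderators". Quiet PWC is the only variable the text names as a moderator.

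No section describes a separate quiet baseline, a held-out set of quiet phrases, or removal of the quiet rows when quiet PWC is the moderator. The only interaction model shown, in the Aim 2 power code, crosses the six-level condition factor with a generic variable z and keeps all six conditions. The code does not identify z as quiet PWC.

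**The concern.** If the moderator is the listener's condition 1 score, or the mean of conditions 1 and 2, the same measurement error stands on both sides of the regression in the quiet rows, but only on the predictor side in the noise and IBM rows. The condition-by-quiet-PWC interaction then contains regression to the mean, whatever IBM does.

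With no true moderation, a significant negative interaction could be read as IBM restoring intelligibility less well for listeners with better baseline perception. If IBM truly restores more for those listeners, the shift can cancel the effect. If it truly restores less, the effect is exaggerated. The study is meant to inform a larger grant proposal, so a false or hidden moderator would carry forward.

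**Working it through.** **The plan's own figure.** The plan gives no figure for this interaction. The nearest is the Aim 2 power of 0.91. Re-implementing the code's data generator and interaction coefficients (0.2, 0.2, 0.3, 0.3, 0.4), with a chi-square approximation for the 5-df interaction because simr was not available, gave about 1.00, not 0.91. That is a separate matter and nothing below rests on it. The code draws z independently of the listener effect and the residual, so it cannot show the problem either way.

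**Inputs.** From the power code: 30 listeners, six conditions, condition effect 0.5, listener SD 2 and residual SD 1. Alpha is .05, taken as two-sided. The listener value is labelled a variance but used as an SD, so the variance is 4 and the ICC is 4/(4+1) = 0.80. These are placeholders; the plan gives no reliability for PWC. Equal variances across conditions are assumed.

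**Closed form.** Let Y_ij = mu_j + b_j·u_i + e_ij, with b = 1 in quiet and M the quiet score.

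- M = Y1: the slope of Y1 on M is 1. The slope of IBM on M is b × 4/(4+1) = 0.80b.
- M = mean of Y1 and Y2: the slope of each quiet score on M is (4+0.5)/(4+0.5) = 1. The slope of IBM on M is b × 4/(4+0.5) = 0.89b.
- No moderation (b = 1): the IBM-minus-quiet slope is 0.80 - 1 = -0.20, or 0.89 - 1 = -0.11. With a separate quiet score of the same reliability it is 0.
- True excess +0.25 (b = 1.25): 1.25 × 0.80 - 1 = 0.00, or 1.25 × 0.89 - 1 = 0.11. Separate score: 0.25 × 0.80 = 0.20, or 0.25 × 0.89 = 0.22.
- True excess -0.25 (b = 0.75): 0.75 × 0.80 - 1 = -0.40, or 0.75 × 0.89 - 1 = -0.33. Separate score: -0.20 or -0.22.

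**Simulated rejection rates with no true moderation, nominal 5%.** Within-listener model, 20,000 replicates; the 11-df row used 5,000.

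| Test | Condition 1 as score | Mean of 1 and 2 as score | Separate score |
|---|---|---|---|
| IBM vs quiet by quiet PWC, dysarthric | 40% | 15% | 5% |
| IBM vs quiet by quiet PWC, control | 5% | 14% | about 5% |
| Omnibus interaction, 5-df F | 35% | 16% | 5% |
| Aim 2 comparison as coded, 11-df likelihood ratio | 31% | 17% | 8% |
| IBM vs noise by quiet PWC | 5% | 5% | not needed |

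Nearly all the false dysarthric rejections are negative. A REML mixed model with six extra covariates (200 runs, condition 1 as score) gave a slope of -0.19 and 39.5% rejection. The coded comparison has 11 df because the reduced model also drops the six covariates (5 + 6); its 8% is small-sample excess of the likelihood-ratio test.

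**Masking.** At a true excess of +0.25 (6,000 replicates), rejection is 6% (condition 1) or 15% (mean), against 40% or 43% with a separate score.

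**Range.** Over assumed ICCs of 0.5, 0.7 and 0.9, the omnibus rate is 82%, 53% and 18% with condition 1, and 49%, 26% and 10% with the mean. If the listener value of 2 is read as a variance, reliability with condition 1 is 2/(2+1) = 0.67, the null shift is -0.33 and the dysarthric contrast rejects in 60% of trials.

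**The case against.** The source of the quiet score is inferred. The plan refers to an adjusted model in a Research Strategy that is not among the documents and might define it. The plan also collects other measures outside the six conditions, so a separate quiet baseline is possible. Nor does any sentence say that the IBM-versus-quiet gap will be tested for moderation by quiet PWC. The comparison of particular interest is IBM versus noise, which is unaffected, and quiet PWC as a listener-level main effect leaves condition contrasts unchanged in balanced data. This stands, and it is why the finding is conditional. But no other quiet score is described, the quiet rows are in these models, and the omnibus interaction is affected even if nobody singles out IBM versus quiet.

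The size also depends on assumptions. At an ICC of 0.95 the omnibus rate is only 11% (condition 1) or 7% (mean). Unequal variances can offset the shift: if the whole spread in quiet is 80% of that under IBM, the condition 1 slope under IBM is (0.8 × 4)/(0.64 × 5) = 1.00, the interaction averages about 0.00 and rejection is 6%. That offset would be an accident of scale; the shift relative to a separate score remains negative. Ceiling effects in quiet were not modelled. So the rates are illustrations, while the direction of the shift is algebra.

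**Conclusion.** The concern holds, on condition that the moderator comes from conditions 1 and/or 2. Relative to a separate quiet score of equal reliability, the IBM-versus-quiet interaction is then shifted by reliability minus 1, which is negative whenever the score contains error. At the power code's SDs this is enough to make false moderation common and to hide a true positive excess of 0.25 completely (condition 1) or by half (mean). Larger positive effects are reduced rather than hidden.

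The reach is limited. With condition 1 alone as the score, only the dysarthric IBM-versus-quiet contrast, the contrast pooled over speech types and the omnibus test are affected. With condition 2 alone, the control contrast takes the place of the dysarthric one. With the mean, both speech types are affected. The main IBM-versus-noise comparison is not compromised, and its moderation test keeps its 5% level. The point should be fixed before analysis; confidence is medium because the plan does not define the score or give its reliability.

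**What to change.** State how the quiet score is computed. When quiet PWC is the moderator, use only conditions 3 to 6 as outcome and test processing (IBM versus noise) by quiet PWC; in simulation this rejects in 5% of null trials with either score. Test IBM versus quiet in a model without the quiet-PWC interaction; quiet PWC may stay as a listener-level main effect.

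If moderation of the IBM-minus-quiet gap is itself of interest, compute the moderator from quiet phrases not used as outcome, for example one half, and regress each listener's IBM score minus the other-half quiet score on it. This also holds the 5% level.

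The cost is SAP wording and a changed model formula, with no new data. Splitting makes both the moderator and the quiet outcome noisier. If the residual variance is phrase sampling, halving the phrases doubles it, so reliability falls from 0.80 to 4/(4+2) = 0.67 (condition 1) or from 0.89 to 4/(4+1) = 0.80 (mean). Power for a true dysarthric slope excess of 0.25 is then only 22% or 26%. The number of phrases per condition is not given, so whether a split is practical is for the investigators to judge. Without a split or a separate quiet measure, the plan should say that this moderation will not be tested.

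### A non-significant difference between IBM-processed speech and speech in quiet is read as restored intelligibility, with no margin set

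*Combined protocol and SAP*

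**What the plan says.** The section Statistical Design and Power attaches two conclusions to the condition contrasts. The first is benefit over noise: "Of particular interest is whether the IBM-processed speech is significantly more intelligible than unprocessed speech in noise". The second is restoration: "These models will also test whether IBM-processed speech is not significantly different from unprocessed speech in quiet". The plan then says what that result would mean: "which would provide evidence that IBM processing restores intelligibility of speech in noise to that of speech in quiet".

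The Study Protocol section defines the quiet reference: "Conditions 1 and 2 will consist of the unprocessed phrases representing dysarthric (condition 1) and control speech (condition 2) in quiet". Conditions 5 and 6 are the IBM-processed dysarthric and control phrases, so the restoration comparisons are 5 versus 1 and 6 versus 2. The plan does not say whether these are tested separately or pooled.

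On size and power it says "For Aim 1, a minimum of 30 participants will be tested per sub-experiment" and reports "for alpha of .05, with 6 covariates, effect size of .5, power = .93". The R code in the same section sets the Aim 1 condition effects, the smallest being "fixef(fit2)[2:3] <- 0.15". No margin, equivalence or non-inferiority test, or confidence-interval criterion for restoration appears in the posted text.

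**The concern.** The plan writes out an inference from non-significance to equality. A two-sided test of no difference can fail to reject because the difference is negligible or because the contrast is imprecise, and the rule does not separate the two. Its incentive also runs the wrong way: testing only the minimum of 30 listeners, or having noisier scores, raises the chance of concluding restoration.

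Restoration is one of the two conclusions the plan draws from these contrasts, and the Study Protocol says the project is meant to inform a large-scale proposal. A restoration claim resting on a null result could be carried into that proposal although a real shortfall remains.

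**Working it through.** **The plan's own power figure.** The Aim 1 code sets the six condition effects to 0, 0.15, 0.15, 0.30, 0.30 and 0.45. The seed-843 data set was rebuilt by emulating R's generator in Python, and the random-intercept model was simulated 4,000 times. The overall 5-df F test of any difference among conditions has power 0.937 (0.946 analytically), close to the stated .93; the likelihood-ratio version gives 0.952. Reading the effect size of .5 as a single pair does not reproduce .93. It gives 0.49 for two independent means with SD 1, 0.78 for a paired test with SD of the difference 1, and over 0.99 under the code's variances. The power call names no pairwise or equivalence test, so the .93 does not describe how precise an IBM-quiet contrast would be.

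**Inputs.**
- From the text: 30 listeners, alpha .05. Two-sided testing is assumed, as the plan does not state it.
- From the code: six measures per listener, between-listener SD 2, residual SD 1, slope 0.5 over levels 1 to 6, response divided by its total SD, six covariates.
- Residual SD on the scaled response: 1/√(0.25 × 35/12 + 4 + 1) = 1/√5.729 = 0.418 as the population value; 0.408 in the seed-843 fit.
- Residual degrees of freedom: 180 − 30 − 5 − 6 = 139.

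**Standard errors.**
- One pair: residual SD × √(2/30) = 0.105 to 0.108.
- Both speech types pooled: residual SD × √(1/30) = 0.074 to 0.076.

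**Chance that a true shortfall is non-significant** (noncentral t, 139 df). The first two result columns use residual SDs of 0.408 and 0.418. The last uses the central 95% range of the residual SD, 0.345 to 0.521, over 2,000 data sets drawn from the code's generator.

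| True shortfall (total SD) | One pair | Pooled | One pair, generator range |
|---|---|---|---|
| 0.15 | 71-72% | 48-50% | 61-80% |
| 0.20 | 53-55% | 24-26% | 39-69% |
| 0.30 | 19-21% | 2-3% | 8-40% |
| 0.45 | 1-2% | not computed | not computed |

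Full-model simulation at 0.15 SD agrees: 0.713 for condition 5 versus 1 and 0.716 for 6 versus 2. If both pairs have that shortfall, both are read as restored in 51% of runs. The code's comments call the values 2 and 1 variances, although they are used as SDs. Read as variances, they give a residual SD of 1/√(0.729 + 2 + 1) = 0.518 and a rate of 80% at 0.15.

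**Effect of precision (one pair).** At 0.20 SD the rate is 53-55% with 30 listeners and 24-26% with 60. At 0.30 SD, a residual SD 1.5 times larger raises it from 19-21% to 53-55%.

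**PWC scale.** The plan gives no SD in PWC points. If it were 10 to 25 points (assumption), 0.15 SD would be 1.5 to 3.75 points and 0.30 SD would be 3.0 to 7.5 points.

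**The case against.** The strongest reply is that the 71-72% figure depends on a chosen shortfall. The plan never names 0.15 SD as an IBM-quiet difference. It is the smallest non-zero effect in the Aim 1 code, whose levels are not mapped to conditions. If levels 1 to 6 were conditions 1 to 6, the code would place IBM 0.30 SD above quiet. The rate falls quickly at larger shortfalls and when the two speech types are pooled. Nor is 0.15 SD shown to matter: under a margin of 0.30 SD it would count as acceptable. All of this stands. The percentages illustrate how the rule behaves; they become false-claim rates only once a margin says which shortfalls are unacceptable.

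It can also be said that this is a proof-of-concept study, that the benefit over noise is the comparison of particular interest, and that the restoration wording is cautious. Those points argue for a modest claim or a wide margin. They do not make a null result evidence of equality.

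The plan cites a Research Strategy that is not in the posted documents, so the absence of a criterion is established for the posted text only. The inference itself, however, is stated in full there.

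Finally, reporting the estimate and interval with no restoration claim would also remove the flaw. That is correct, and it is the fallback if no margin can be justified.

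**Conclusion.** The concern holds. The rule is invalid as written and should be replaced before data are seen. The logical defect does not depend on any chosen shortfall: any true deficit that is small relative to the standard error will usually be read as restored, and less precision makes this more likely.

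The size rests on the code's variances, 30 listeners, one IBM-quiet pair and a two-sided 5% test. On that basis a 0.15 SD shortfall passes as restored about 7 times in 10, a 0.30 SD shortfall about 1 time in 5, and a 0.45 SD shortfall almost never. The units are total SDs of a simulated response not tied to PWC data, so these figures should not be carried over to PWC points. The IBM-versus-noise conclusion is not affected.

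**What to change.** Replace the rule with a non-inferiority analysis of IBM minus quiet from the mixed model, done separately for dysarthric speech (condition 5 versus 1) and control speech (6 versus 2). Fix and justify a margin in PWC points before data are seen. Claim restoration for a speech type only if the lower limit of the two-sided 95% confidence interval (one-sided 2.5%) lies above minus the margin. Otherwise report the estimate and interval without a restoration claim.

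Name the model that supplies the contrast. The plan lists unadjusted and adjusted models and also uses quiet PWC as a covariate and moderator; if quiet PWC moderates the condition effect, there is no single IBM-minus-quiet difference.

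**Planning figures** (one pair, 30 listeners, true difference zero, code variances). The margin with 80% power is SE × (1.960 + 0.842) = 0.295 to 0.302 SD, or 0.297 to 0.304 with t quantiles. For comparison, it is 0.26-0.27 SD at one-sided 5%, and 0.31-0.32 SD for two one-sided tests at 5% each. At one-sided 2.5% with residual SD 0.418, power is 28%, 46% and 79% for margins of 0.15, 0.20 and 0.30 SD, and 80% power needs about 122, 69 and 31 listeners. These should be recomputed once a PWC-scale SD is available.

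**Cost.** The change needs revised SAP wording and a justified margin, and the margin takes some work because the plan has no PWC SD. The data and listeners stay the same. The restoration claim becomes harder to make, and with 30 listeners a margin tighter than about 0.30 SD has less than 80% power. Even at 0.30 SD, a true shortfall of 0.05 SD lowers power to 63-66%.
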